8.3 Definitions of analysis sets

8.3.1 Efficacy analysis set

The full analysis set (FAS) will include all randomised patients. The full analysis set will be used for all efficacy analyses and treatment groups will be compared on the basis of randomised study treatment, regardless of the treatment actually received.

8.3.2 Safety analysis set

The safety analysis set (SAS) will consist of all patients who received at least one dose of study treatment. Safety data will not be formally analysed but summarised using the safety analysis set, according to the treatment received; i.e., erroneously treated patients (e.g., those randomised to treatment A but actually given treatment B) will be summarised according to the treatment they actually received.

8.3.3 PK analysis set

Pharmacokinetic Analysis Set is defined as patients in the FAS who have at least one measurable PK concentration, supported by the relevant date and time of this sample. For each time a PK sample was taken from a subject, the dosing data for that day and for multiple dosing, the dose date for the 2 days prior to the sample days must be available. For any individual sample from a subject to be included in the PK analysis set, the full sample data and dosing data need to be present for that sample/subject.

The pharmacokineticist will agree to the strategy for dealing with data affected by protocol deviations before any formal statistical analysis is performed. Important protocol deviations include changes to the procedures that may impact the quality of the data or any circumstances that can alter the evaluation of the PK. Examples include, but not limited to, vomiting following oral dosing occurring within the timeframe of 2 times the median t_{max} ; sample processing errors that lead to inaccurate bioanalytical results; incomplete dose administered; incomplete PK profile collected; and/or use of disallowed concomitant medication. In the case of an important protocol deviation or event, affected PK data collected will be excluded from the summaries and statistical analyses, but will still be reported in the study result listings. Important deviations will be listed and summarised in the CSR.

8.4 Outcome measures for analyses

8.4.1 Calculation or derivation of efficacy variables

8.4.1.1 DFS

DFS is defined as the time from the date of randomisation until the date of disease recurrence or death (by any cause in the absence of recurrence).

Patients who are disease-free and alive at the time of analysis will be censored at the date of their last follow-up assessment. The DFS time will always be based on scan/assessment dates and not visit dates. If assessments contributing towards a particular visit are performed on different dates, for example, a biopsy confirming disease recurrence following the scan where recurrence was suspected, the date of recurrence will be the earliest of the dates of the assessment that triggered the recurrence.

DFS rate at 2, 3, 4 and 5 years is defined as the proportion of patients alive and disease free at 2, 3, 4 and 5 years, respectively, estimated from Kaplan Meier plots of the primary endpoint of DFS at the time of the primary analysis.

8.4.1.2 OS

OS is defined as the time from the date of randomisation until date of death due to any cause. Any patient not known to have died at the time of analysis will be censored based on the last recorded date on which the patient was known to be alive.

Note: Survival calls will be made in the week following date of DCO for IDMC and in the two weeks following date of DCO for primary analysis and subsequent analyses and if patients are confirmed to be alive or if the death date is post the DCO date these patients will be censored at the date of DCO. Death dates may be found by checking publicly available death registries.

OS rate at 2, 3, 4, and 5 years is defined as the proportion of patients alive at 2, 3, 4, and 5 years respectively, estimated from a Kaplan Meier plot of OS at the time of the primary analysis and any further timepoints. Long-term OS data captured in the long-term OS follow-up will be analysed as described in Section 8.8.

8.4.1.3 Progression-free survival (PFS) (exploratory)

PFS is defined as the time from the date of randomisation to the date of disease progression or death. Patients alive and for whom a disease progression has not been observed should be censored at the last time known to be alive and without a disease progression; i.e., censored at the last progression assessment date if the patient has not had a progression or death.

8.4.1.4 Time to first subsequent therapy or death (exploratory)

Time to first subsequent therapy (TFST) or death is defined as the time from the date of randomisation to the earlier of the date of anti-cancer therapy or procedure start date following

study drug discontinuation, or death. Any patient not known to have had a subsequent therapy/procedure or not known to have died at the time of the analysis will be censored at the last known time to have not received subsequent therapy; i.e., the last follow-up visit where this was confirmed.

8.4.1.5 Time to second subsequent, therapy or death (exploratory)

Time to second subsequent therapy (TSST) or death is defined as the time from the date of randomisation to the earlier of the date of second subsequent anti-cancer therapy or procedure start date following study drug discontinuation, or death. Any patient not known to have died at the time of the analysis and not known to have had a second subsequent therapy/procedure will be censored at the last known time to have not received second subsequent therapy, i.e., the last follow-up visit where this was confirmed.

8.4.1.6 Brain metastases

The number of patients developing brain metastasis during the study treatment will be summarised.

8.4.1.7 Health-related Quality of Life and symptoms

Subjects will complete a paper version of the SF-36 v2 questionnaire. The SF-36 v2 is a validated instrument for measuring a person's general health status (Ware et al, 1993) over the past 28 days. The SF-36 v2 includes 8 domains Physical Functioning (PF); Role Limitations-Physical (RP), Vitality (VT), General Health Perceptions (GH), Bodily Pain (BP), Social Function (SF), Role Limitations-Emotional (RE), and Mental Health (MH) and can be summarised into 2 summary scores, the Physical Component Summary (PCS) and Mental Component Summary (MCS). Final scores for each scale range from 0-100 with higher scores indicating better health. The general population has a mean score of 50 with a standard deviation of 10.

The absolute values and change from baseline will be calculated for each domain and summary scale at each post-baseline assessment.

8.4.1.8 Health Resource Use Module

The Health Resource Use Module will be assessed in terms of symptoms for admission and type of admission (planned/unplanned hospitalisation, outpatient visits, or emergency department visits).

8.4.2 Calculation or derivation of safety variables

Safety and tolerability will be assessed in terms of AEs, deaths, laboratory data, vital signs (pulse and BP), ECG, LVEF, WHO performance status, and ophthalmologic assessment. These will be collected for all patients.

8.4.2.1 Adverse events

Adverse events (both in terms of Medical Dictionary for Regulatory Activities [MedDRA] preferred terms and CTCAE grade) will be listed individually by patient.

Any AE occurring before treatment with study drug will be included in the data listings but will not be included in the summary tables of AEs.

Any AE occurring within 28 days of discontinuation of study drug (i.e., the last dose of AZD9291/placebo) and prior to the start of a new anti-cancer treatment will be included in the AE summaries. Any events in this period that occur after a patient has received further therapy for cancer (following discontinuation of study drug) will be flagged in the data listings. Please refer to Section [6.3.1](#).

8.4.2.2 Other significant adverse events

During the evaluation of the AE data, an AstraZeneca medically qualified expert will review the list of AEs that were not reported as SAEs and AEs leading to discontinuation. Based on the expert's judgement, significant AEs of particular clinical importance may, after consultation with the Global Patient Safety Physician, be considered other significant AEs (OAEs) and reported as such in the CSR. A similar review of laboratory/vital signs (pulse and BP)/ECG data will be performed for identification of OAEs.

Examples of these are marked haematological and other laboratory abnormalities, and certain events that lead to intervention (other than those already classified as serious), dose reduction or significant additional treatment.

8.4.3 Calculation or derivation of pharmacokinetic variables

Pharmacokinetic analysis of the plasma concentration data for AZD9291 and its metabolites will be performed by or on behalf of Quantitative Clinical Pharmacology (QCP), AstraZeneca.

Plasma concentrations will be listed and summarised by sampling interval in the CSR. The ratio of metabolite to AZD9291 will also be calculated and summarised.

Pharmacokinetic data from this study will be analysed using a population PK approach, which may include exploring the influence of covariates on PK, if the data allow. The data collected in this study may also be combined with similar data from other studies and explored using population PK and/or pharmacokinetic-pharmacodynamic methods. The results of any such analyses will be reported separately from the CSR.

8.5 Methods for statistical analyses

All efficacy analyses will be performed on the FAS population. Results of all statistical analyses will be presented using a 95% confidence interval (CI) and 2-sided p-value.

8.5.1 Analysis of the primary variable(s)

DFS in the subset of patients with stage II-III A cancer will be analysed using a log rank test stratified by stage (II, IIIA), mutation type (Ex19Del, L858R either alone or in combination with other EGFR mutations) and race (Asian, Non-Asian) for the generation of the p-value and using the Breslow approach for handling ties. DFS in the overall population will be analysed using a long rank test stratified by stage (IB, II, IIIA), mutation status (Ex19Del, L858R either alone or in combination with other EGFR mutations as confirmed by a central test) and race (Asian, Non-Asian) for the generation of the p-value. The hazard ratio and confidence interval will be obtained directly from the U and V statistics as follows ([Berry et al 1991](#), [Selke and Siegmund 1983](#)):

$$HR = \exp(U/V)$$

$$95\% \text{ CI for HR} = (\exp\{U/V - 1.96/\sqrt{V}\}, \exp\{U/V + 1.96\sqrt{V}\})$$

Where $U = \sum_i (d_{1i} - e_{1i})$ is the log-rank test statistic (with d_{1i} and e_{1i} the observed and expected events in group 1) and \sqrt{V} the standard deviation of the log-rank test statistic obtained from the LIFETEST procedure with a STRATA term for the stratification variables.

A Kaplan-Meier (KM) plot of DFS will be presented by treatment group.

The assumption of proportionality will be assessed. In the event of non-proportionality, the HR will be interpreted as an average HR over the observed extent of follow-up. Proportionality will be tested firstly by examining the plots of complementary log-log (event times) versus log(time) and, if necessary, a time-dependent covariate will be fitted to assess the extent to which this represents random variation.

Sensitivity analyses

(a) Quantitative interactions

The presence of quantitative interactions will be assessed by means of an overall global interaction test. This will be performed by comparing the fit of a Cox proportional hazards model including treatment, all covariates, and all covariate-by-treatment interaction terms, with one that excludes the interaction terms and will be assessed at the 2- sided 10% significance level. If the fit of the model is not significantly improved then it will be concluded that overall the treatment effect is consistent across the subgroups.

If the global interaction test is found to be statistically significant, an attempt to determine the cause and type of interaction will be made. Stepwise backwards selection will be performed on the saturated model, whereby (using a 10% level throughout) the least significant interaction terms are removed one-by-one and any newly significant interactions re-included until a final model is reached where all included interactions are significant and all excluded interactions are non-significant. Throughout this process all main effects will be included in the model regardless of whether the corresponding interaction term is still present. This

approach will identify the factors that independently alter the treatment effect and prevent identification of multiple correlated interactions.

Any quantitative interactions identified using this procedure will then be tested to rule out any qualitative interaction using the approach of Gail and Simon 1985. ([Gail and Simon 1985](#)).

(b) Evaluation-time bias

In order to assess possible evaluation-time bias that could occur if scans are not performed at the protocol-scheduled time points, the midpoint between the time of recurrence and the previous evaluable assessment will be analysed using a log rank test stratified by stage, mutation status and race.

(c) Attrition bias

Possible attrition bias will be assessed by repeating the primary DFS analysis, except that the actual DFS times rather than the censored times of patients who recurred or died in the absence of recurrence immediately following 2 or more non-evaluable assessments, will be included. In addition, patients who take subsequent therapy prior to recurrence or death will be censored at their last evaluable assessment prior to taking the subsequent therapy. A Kaplan-Meier plot of the time to censoring, where the censoring indicator of the primary DFS analysis is reversed, will be presented.

There is no prospective central radiology review planned for this study. A central review of equivocal cases by a review committee may be conducted. A retrospective radiology review of all cases may also be undertaken.

There is no prospective central pathology review planned for this study. A retrospective review may be undertaken.

Subgroup analyses

Subgroup analyses will be conducted by comparing DFS between treatments in the following groups:

- Stage (IB, II, IIIA)
- EGFR mutation type (Ex19Del, L858R either alone or in combination with other EGFR mutations)
- EGFR mutation status detectable in plasma-derived circulating tumour deoxyribonucleic acid (ctDNA) (Ex19Del, L858R)
- Pre-treatment T790M (amino acid substitution at position 790 in EGFR, from a threonine to a methionine) mutation status (Positive, Negative)
- Race (Asian, Non-Asian)
- Adjuvant chemotherapy (Yes, No)

- Gender (Male, Female)
- Age at randomisation (<65, \geq 65)
- Smoking history (Never, Ever).

The Breslow approach for handling ties will be used for Cox regression model in subgroup analysis.

8.5.2 Analysis of the secondary variable(s)

8.5.2.1 DFS rate

Kaplan-Meier plots will be produced to assess if recurrence rates have reached an apparent plateau. Estimates of DFS rate at 2, 3, 4 and 5 years obtained from the plot will be presented for each arm. If the shape of the DFS curve suggests a plateau, a cure rate model may also be fitted. From this, estimates of cure can be made for each arm.

8.5.2.2 OS

OS data will be analysed using a log rank test stratified by stage (IB, II, IIIA), mutation type (Ex19Del, L858R either alone or in combination with other EGFR mutations) and race (Asian, Non-Asian) for the generation of the p-value and using the Breslow approach for handling ties. The hazard ratio and confidence interval will be obtained directly from the U and V statistics, as described in Section 8.5.1 (provided there are sufficient events available for a meaningful analysis (>20 deaths), if not descriptive summaries will be provided).

A Kaplan-Meier plot of OS will be presented by treatment group.

Additional exploratory analysis of overall survival adjusting for the impact of subjects randomised to placebo who subsequently receive an EGFR-TKI for sensitising mutations and T790M may be conducted if this treatment sequence occurs in a proportion of subjects. Methods such as Rank Preserving Structural Failure Time (RPSFT) ([Robins and Tsiatis 1991](#)), Inverse Probability of Censoring Weighting (IPCW) ([Robins and Finkelstein 2000](#)) and other methods in development may be explored. An OS analysis in centres where no access to a T790M directed EGFR-TKI may also be performed. The decision to adjust and final choice of methods will depend on the observed data and the plausibility of the underlying assumptions.

8.5.2.3 OS rate

OS rate at 2, 3, 4, and 5 years will be estimated for each arm from a Kaplan-Meier plot of OS.

8.5.3 Analysis of health-related quality of life

The scores for each of the 8 health domain scores and for each of the physical and mental component summary measures from the SF-36 v2 will be summarised in terms of mean changes from baseline at each post-baseline assessment.

8.5.4 Futility analysis

The IDMC will conduct a futility analysis. Further details will be documented in the IDMC Charter prior to the first DMC safety review meeting. An IDMC will review the futility outcomes and provide a recommendation for whether the study should continue, stop or be modified in some way. The IDMC will also review safety on an ongoing basis.

8.6 Impact of COVID-19

Depending on the extent of any impact, summaries of data relating to patients diagnosed with COVID-19, and impact of COVID-19 on study conduct (in particular missed visits, delayed or discontinued IP, and other protocol deviations) may be generated. More detail will be provided in the SAP.

8.7 Further analysis post IDMC7

Following the recommendation of the IDMC after their 7th meeting, an interim analysis was conducted with a DCO of 17 January 2020 ([Wu et al 2020](#)). Please see Section 1.4 and text below for full details.

Given the study has been unblinded and reported earlier than planned, the following further analysis will be conducted.

DFS

An exploratory analysis of DFS in the stage II-IIIA population will be conducted when approximately 247 DFS events have been observed. At this time, an analysis of DFS in the overall population will also be conducted (exploratory in nature). If there are less than 63 DFS events in the stage IB population at this time, follow-up for DFS will continue and a further exploratory analysis in the overall population will be conducted when at least 63 DFS events have occurred in the stage IB patients. Safety data, TFST, TSST and PFS may also be reported at this time(s).

OS

The final OS analysis will be conducted when approximately 94 OS events have been observed in the stage II-IIIA population (approximately 20% maturity). At this time, the final OS analysis will also be conducted in the overall population. A further exploratory analysis of OS landmarks at 3, 4 and 5 years may be conducted after this final OS analysis. Safety data may also be reported at this time(s).

8.8 Long-term OS analysis - study extension

A long-term OS analysis from the time of randomisation until date of death due to any cause will be conducted to obtain long-term follow-up OS data. Overall survival data captured during the study extension (up to approximately 10 years after the last patient is randomised) will be analysed using the methods stated in Section 8.5.2.2 and Section 8.5.2.3 above, as

appropriate. The formal statistical analysis is complete and p-values will not be calculated for this follow-up analysis.

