Patients will be initially followed as per the study protocol until data cut-off for the primary analysis, estimated as 68-70 months following first subject randomised, based on a 28 month recruitment period. Results from the primary analysis will be reported in the Clinical Study Report. If there are meaningfully less than 70 DFS events in the IB population at the time of the primary analysis, further follow up of all patients according to the same study plan will be performed until completion of the final exploratory DFS analysis (hereafter referred to as the 'final DFS analysis').

Following the primary analysis (or 'until completion of final DFS analysis' if required), patients will be followed-up for survival according to a reduced study plan (OS period) until the data cut-off for the final OS analysis.

Following the final OS analysis, the ADAURA study was planned to be closed, and the collection of survival, cancer therapy, and safety data for globally recruited patients no longer on study treatment was to stop entirely. All patients and Investigators remain blinded to individual study treatment allocation. Following the final OS analysis, CSP edition 6 has introduced a further optional long-term OS follow-up. All patients in survival follow-up will be offered the opportunity to participate in the long-term OS follow-up. Patients who consent to participate will be followed yearly for survival until approximately 10 years after the last patient is randomised to capture long-term OS data in the study extension. Safety data (all serious or non-serious events of ILD/pneumonitis and cardiac failure, and all SAEs) for patients who are treated with open-label osimertinib will be collected as described in Section 6.3. Any patients still on open-label osimertinib and deriving clinical benefit can continue to receive treatment until they meet a discontinuation criteria, as outlined in Section 3.10. Following the completion of the study extension, any patients still on open-label osimertinib will be managed outside of the study per Section 7.3.3. At this point, any SAEs will be reported outside of the database, only reported as per Section 6.4 and Section 6.5.

Objectives

Primary Objective	Outcome Measure
To assess the efficacy of AZD9291 compared to placebo as measured by disease free survival (DFS)	
 DFS by investigator assessment
Secondary Objective:	Outcome Measure:

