3.11 Criteria for withdrawal from study

At any time, patients are free to withdraw from the study without prejudice to further treatment. A patient who decides to discontinue IP treatment and follow-up assessments will always be asked about the reason(s) and the presence of any AEs. If possible, they will be seen and assessed by an Investigator. Adverse events will be followed up ([See Section 6.3.2](#)); all IPs should be returned by the patient or caretaker.

If patients wish to withdraw their consent to both study drug and study assessments, they should be asked if they are willing to continue with survival follow-up (which can be conducted by telephone). If patients wish to withdraw their consent to further participation in the study entirely, including survival follow-up, this should be clearly documented in the patient notes, “Informed Consent Form addendum – options for withdrawal of consent” and in the clinical study database.

For the OS endpoints, the status of ongoing, withdrawn (from the study), and “lost to follow-up” patients at the time of the primary analysis and final OS analysis, and also at the time of the long-term OS analysis for patients who consent to long-term OS follow-up, should be obtained by the site personnel by checking the patient’s notes, hospital records, contacting the patient’s current physician, and checking publicly available death registries. In the event that the patient has actively withdrawn consent to the processing of their personal data, the vital status of the patient can be obtained by site personnel from publicly available resources where it is possible to do so under applicable local laws.

Withdrawn patients will not be replaced.

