4.3.4 Survival follow-up (up to final OS analysis)

Assessments for survival should be made every 24 weeks up to 5 years (264 weeks) after randomisation and yearly thereafter following disease recurrence. Survival information may be obtained via telephone contact with the patient, patient's family or by contact with the patient's current physician.

In addition to the survival status, the following assessments are required post recurrence as detailed in the study plan ([Table 2](#)).

- Anti-cancer therapy, radiotherapy and surgery
- Serious Adverse event collection (causally related)
- Subsequent response and progression data (PFS) in accordance with local practice until the first confirmed disease progression on a subsequent treatment (not collected post primary analysis or post 'Final DFS analysis' if required)

Survival data will be collected up to the time of the final OS analysis. Patients should be contacted in the week following date of DCO for IDMC and in the two weeks following date of DCO for primary analysis and subsequent analyses. The status of ongoing, withdrawn (from the study), and "lost to follow-up" patients at the time of each of the efficacy analyses should be obtained by the site personnel by checking the patients notes, hospital records, contacting the patient's general practitioner, and checking publicly available death registries. In the event that the patient has withdrawn consent to the processing of their personal data, the survival status of the patient can be obtained by site personnel from publicly available resources where it is possible to do so under applicable local laws.

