5.1.3 Overall Survival

Overall survival is defined as the time from randomisation to the date of death (from any cause) or to the date the patient was last known to be alive.

Following randomisation and up to final OS analysis, patients will be followed up for survival every 24 weeks for 5 years (264 weeks) and then yearly thereafter, until the study is closed.

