5.1.3.1 Overall survival – long-term OS survival

Following the final OS analysis, patients who consent to participate in long-term OS follow-up will be followed yearly for survival until approximately 10 years after the last patient is randomised.

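### Does the missing rule for the interval between the final OS cut-off and extension consent distort the long-term survival curve?

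*Protocol*

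**What the plan says.** Protocol 8.8 states that OS data from the extension "will be analysed using the methods stated in Section 8.5.2.2 and Section 8.5.2.3 above", as appropriate. Those sections are the stratified log-rank analysis with its hazard ratio, and Kaplan-Meier rates at 2, 3, 4 and 5 years. Section 8.8 adds: "The formal statistical analysis is complete and p-values will not be calculated for this follow-up analysis".

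The synopsis and Sections 1.6 and 4.5 give the order of events: "Following the final OS analysis, CSP edition 6 has introduced a further optional long-term OS follow-up". Section 4.1.1.1 requires a separate written consent for it.

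On whose survival status is collected after the final OS analysis, the sections differ.

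- **Pointing to consenters only.** Section 3.11 asks for status "at the time of the long-term OS analysis for patients who consent to long-term OS follow-up". Section 4.3.4 says "Survival data will be collected up to the time of the final OS analysis". Section 5.1.3.1 says "Following the final OS analysis, patients who consent to participate in long-term OS follow-up will be followed yearly for survival". Section 9.3 treats non-consenters as having completed the study at their last visit before the final OS analysis.
- **Carrying no such limit.** Sections 4.3.5 and 4.5, written for the extension, tell sites to establish the status of ongoing, withdrawn and lost patients from notes, hospital records, the general practitioner and death registries. Section 8.4.1.2 censors a patient only if not known to have died, at the last date known alive, and allows death dates from registries. Section 5.1.3 says "Following randomisation and up to final OS analysis, patients will be followed up for survival" every 24 weeks for 5 years "and then yearly thereafter, until the study is closed"; Section 1.6 also runs follow-up to study closure.

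The SAP available is dated 23 June 2020, before the extension existed.

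**The concern.** A patient who died between the final OS cut-off and the extension consent could not consent, and one who consented has by construction survived that interval. If the consenters' time in the interval is counted and the deaths are not, the late curve contains a stretch in which nobody can die. This is immortal time. It acts in the same direction in both arms and does not shrink with sample size.

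Section 8.8 has no rule against this: no delayed entry, no handling of deaths in the interval, no censoring date for those who decline. The extension exists to describe long-term survival, so the level of the late curve is its main product. Even the sign of the error appears open, because it depends on how many of those deaths reach the database relative to how many living patients consent.

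**Working it through.** **The plan's own figure.** SAP 1.3 gives 195 deaths for about 80% power at OS HR 0.66, two-sided 4%. Check: 4 × (2.054 + 0.842)² / (ln 0.66)² = 4 × 8.38 / 0.1727 = 194. This reproduces. The same paragraph assumes a placebo median of 96 months, so the placebo hazard is h = ln 2 / 96 = 0.00722 per month, and 0.66 × 0.00722 = 0.00477 on active.

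**Length of the gap (g).** The documents do not state it. The cut-off is only estimated, as Q1 2023; edition 6.0 is dated 9 August 2023. From 31 March that is 131 days, or 4.3 months; from 1 January, 220 days, or 7.2 months. Consent comes later still, because Section 10.5 requires approval of a revised consent form before use.

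**Direction.** Let p be the share of gap deaths that become known and c the share of living patients who consent. If refusers are censored at the old cut-off, the Kaplan-Meier hazard in the gap is about p/c times the true one: survival is too high if p < c and too low if p > c.

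**No gap death counted (p = 0).** The cumulative hazard omitted at late times is about h·g·c·ln(1/c)/(1−c).

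- Placebo design hazard, g = 7, c = 0.9: 0.0505 × 0.948 = 0.0479. True 10-year survival is exp(−0.00722 × 120) = 0.420. Overstatement: 0.420 × (e^0.0479 − 1) = 2.1 points.
- Assumed low hazard 0.0027, g = 4, c = 0.7: 0.0108 × 0.832 = 0.0090. True survival is 0.723. Overstatement: about 0.7 point.

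**All gap deaths counted, refusers censored at the old cut-off.** The excess cumulative hazard is about h·g·ln(1/c). With the placebo design hazard and g = 7, 10-year survival is understated by 0.420 × (1 − e^−0.0053) = 0.2 point at c = 0.9, and by 0.420 × (1 − e^−0.0180) = 0.75 point at c = 0.7.

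**All gap deaths counted, refusers censored when the extension is offered.** Deaths and risk set are both complete up to that contact, so nothing is omitted or added.

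**With hazards fitted to the trial.** Hazards were fitted to 29 deaths among 682 patients at the January 2020 cut-off (Section 1.4) and to 15 to 20% dead at the final cut-off. The latter is 94 stage II-IIIA deaths (Section 8.7) plus an assumed 8 to 42 in stage IB: 102/682 to 136/682. HR is 0.66 or 0.45 (the crude 9 against 20 deaths). Ranges are points per arm, for a gap of 4.3 to 7.2 months and 70 to 90% consent:

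| Handling of the gap | 5-year OS | 10-year OS |
|---|---|---|
| No gap death counted | +0.2 to +1.1 | +0.7 to +2.5 |
| All counted, refusers censored at old cut-off | 0.0 to −0.4 | −0.1 to −0.9 |
| All counted, refusers censored at the offer | within 0.1 | within 0.1 |

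At 2 to 4 years the effect is below 0.1 point in every row. The hazard ratio changes by less than 0.005 throughout. For scale, the 95% sampling half-width at 10 years, with 341 patients per arm and 57.7% survival, is 1.96 × √(0.577 × 0.423 / 341) = 5.2 points; at 70 to 80% survival it is 4.9 to 4.2.

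**The case for a change.** The strongest case for a change is that the text does conflict. A site following 3.11, 4.3.4 and 9.3 could stop looking for deaths among non-consenters, while a site following 4.3.5 would not. The p = 0 error is systematic, and 10 years is not its peak: the rising fitted hazards give about 0.9 to 4 points at 8 years. The gap could also exceed 7 months. With all deaths counted but refusers censored at the old cut-off, consent of 50% would understate 10-year survival by about 0.6 to 2 points. A rule written now would cost one paragraph.

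What stands is that the sections are not aligned and that 8.8 is silent. The p = 0 case is still a corner. It needs every gap death to stay unknown until about 2029, although all patients in survival follow-up are to be offered the extension, a contact that tends to show who has died. Section 3.11 says whose status must be looked up; it does not remove a known death from the analysis. Section 4.3.4 ends collection at the final OS analysis rather than at its cut-off date. One caveat remains: SAP 3.2.3 takes the last-alive date from the survival module, so a refuser is censored at the offer only if status is entered there at that time.

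The obvious remedy is a trade-off. Re-entering consenters at their consent date also brings the curve within about 0.1 point of complete follow-up, but it leaves known gap deaths out of the main curve, contrary to 8.4.1.2. Vital status to a common date loses no data. Choosing between them is a matter for the SAP.

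**Conclusion.** No change to the plan follows. Section 8.8 leaves a convention unwritten, and applying 8.4.1.2 in the ordinary way fills it: known deaths count, and living patients who decline are censored at the last date known alive. If that date is recorded when the extension is offered, the bias is within about 0.1 point. The error of 0.7 to 2.5 points at 10 years arises only if no gap death is ever counted. If deaths are counted but refusers' alive dates are not updated, the error reverses and is at most about 0.9 point at 70% consent or higher.

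These sizes rest on an assumed gap of 4.3 to 7.2 months, assumed consent of 70 to 90%, fitted or design hazards, and consent unrelated to prognosis, which was not modelled. In all these cases the effect is below the sampling half-width. Of the rates named in 8.5.2.3 only 5-year OS moves, by at most about 1 point. The hazard ratio is unchanged, no test is planned, and formal testing is already finished. An SAP for the 2029 analysis is the natural place to state the convention.
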